- Download Safety Lab results from the CALM website. Copy results (which will appear on two separate lines in the detailed spreadsheet) into the "Safety Labs Template" excel in dopamine > Lithium in FTD > Biological Samples. Convert all values to 'number' in excel so that cell highlighting rules will function. Out of range values will appear pink. Fill in additional information at the bottom of the page using data from the screening visit as a reference. Save in the "Participant Lab Results" folder. You can then EITHER
 - o 1) print this page and obtain a clinician signature in person
 - 2) convert to PDF form and add signature line and comments box, then forward to study clinician for review and signature
 - o 3) Send to study clinician and then have them sign in REDCap
- □ Schedule Week 8 visit with participant for 2 weeks after their week 2 visit.

Week 8

Pre-visit:

- □ Schedule an at-home blood draw via ExamOne, to occur as close to the virtual visit as possible. Notify the CALM lab of the anticipated date of this visit so they can expect the shipment. Remind study partner not to give medication dose morning of blood draw.
- □ Create zoom link & send along with date/time of visit & visit schedule to the study partner
- □ Send a calendar invitation to the study physician. In the calendar invitation, include:
 - o Zoom link
 - o Links to clinician forms within REDCap for the correct subject/week
 - List of clinician forms: Treatment emergent symptoms, CGI-Severity, CGI-Change, Simpson-angus, Lawton, CDR
 - Current subject medication dose, anticipated dose change after visit (unless at max dose of 600mg/day), & any other relevant information

During visit:

- □ Complete medication compliance check: have study partner count pills remaining in the bottle they have been using. Each bottle contains 28 pills, so calculate the number of pills that should be remaining based on dose & time since the last visit.
- On REDCap, complete the following forms with the study partner:
 - Visit registry, concomitant meds, NPI, Stereotypic/Ritualistic behaviors, Zarit
 Burden Interview, study drug issue/return log

Post-visit:

- Following the at-home blood draw, complete a Serum Sham Lithium Level Form (dopamine>Lithium in FTD>Serum-Sham Lithium Levels) and send it to [name], who will send the form to [name] along with the REAL serum lithium level (once it is available on CALM). [name] will then complete the form and send it back to [name], who will send it to you. Save the signed form in a unique subject folder in dopamine>Lithium in FTD>Serum-Sham Lithium Levels.
- If no contradictions per study clinician, AND serum lithium/sham level is within the target window, instruct participant/study partner to stay at OR increase dose to 600mg/day (two pills mornings, two pills evenings), using two new bottles.
- □ Obtain clinician signature on REDCap study drug issue/return log, resolve any missing data from clinician forms, fill out serum-sham lithium level REDCap form.
- □ Schedule Week 10 visit with participant for 2 weeks after their week 2 visit.
- □ If not already done, schedule in-person week 12 visit and submit room request to Irving

Week 10

Note: there is no blood draw associated with this visit unless the medication dose was increased at week 8. If this is the case, follow instructions related to at-home blood draws & serum/sham lithium levels.

Pre-visit:

- □ Create zoom link & send along with date/time of visit & visit schedule to the study partner
- □ Send a calendar invitation to the study physician. In the calendar invitation, include:
 - o Zoom link
 - o Links to clinician forms within REDCap for the correct subject/week
 - o List of clinician forms: Treatment emergent symptoms, CGI-Severity, CGI-Change
 - o Current subject medication dose & any other relevant information

During visit:

- □ Complete medication compliance check: have study partner count pills remaining in the bottle they have been using. Each bottle contains 28 pills, so calculate the number of pills that should be remaining based on dose & time since the last visit.
- On REDCap, complete the following forms with the study partner:
 - Visit registry, concomitant meds, NPI, Stereotypic/Ritualistic behaviors, study drug issue/return log

Post-visit:

- □ Instruct participant/study partner to stay at current dose, using two new bottles.
- Obtain clinician signature on REDCap study drug issue/return log, resolve any missing data from clinician forms.

Week 12

Pre-visit:

- Confirm in-person date & directions with participant, confirm room booking with CRR, confirm event on RA/physician calendars. Remind participant to bring in used study drug kit & all remaining pills. Remind study partner not to give medication dose morning of visit.
- Email NYSPI pharmacy ahead of time to request the Unblinding Envelope; pick this up from the NYSPI pharmacy.
- Prepare a summary of the participant's trajectory through the trial (dopamine>Lithium in FTD> Exit Summaries > TEMPLATE)
- Enter subject ID, date, and coordinator/physician initials on page 1 of the "Week 12 INPERSON Packet" (dopamine>Lithium in FTD>Visit Instruments>In Person), print doublesided. Also prepare and print visit schedule.
- □ Separate into the Clinician forms which can be placed in a blue folder (INCLUDING the unblinding envelope & exit summary) and coordinator forms

- Add paper MDRS and MDRS cards, laminated response option sheets (for FBI & Zarit) to coordinator materials
- Prepare & label blood tubes (1 red, 1 gold, 1 purple) & petty cash + receipt booklet (\$20/visit hr payment, including past virtual visits, + \$40 transportation payment if applicable)

During visit:

- Collect study drug kit
- □ Complete MDRS with patient. Study partner should sit in waiting room or affirm that they will not aid the participant if they stay in the room.
- Complete blood draw in the phlebotomy room ([name] or [name] will perform this). Collect the purple and gold tubes in a biohazard bag (provided by CRR) along with the CALM requisition form. Collect the red tube in a biohazard bag with the Biomarkers Core Laboratory requisition form
 - Drop the Biomarkers Sample in the Biomarkers Core Laboratory (PH10-104): walk past the reception area to the opposite side of the hall from the clinical rooms & through the double doors. On your right several doors in, you will see the entrance to a large lab space with many cubicles. At the entryway, there is a dropoff bin. This must be done before 3:30pm.
 - Then go to the 15th floor to drop off the CALM sample (drop-off bin in room 15-401 in P&S building, down the blue and white hallway)
- □ When you return, obtain the ECG machine from the phlebotomy room and a gown from the closet (in rooms 2&4) or drawer under the exam table (rooms 3&5). Close the door blinds and draw the curtain by the exam bed. Have the participant change into the gown with their top clothes removed and the gown tied with the opening in front. Lie the participant down on the exam bed and then place the leads on the sternum and below the ribs and connect the ECG machine as trained. If you are not trained, [name], [name], or the study physician may complete the ECG.
- Once the participant is dressed and the ECG machine is retuned, you may EITHER 1) complete the NPI, FBI, and Zarit with the caregiver (preferred) or 2) move on and schedule a time within 3 days to complete these by phone or zoom. If completing in person, it is helpful to provide the response options (printed in a laminated sheet), and if completing virtually, you may email these to the caregiver in advance.
- □ Pay the study partner (\$20/visit hour, including from virtual visits + \$40 for transportation if relevant) and complete/sign a petty cash receipt.
- The clinician portion of the visit should be conducted LAST and will include the unblinding & planning for future care. Note that the study RA should remain blinded even after the participant completes the trial, so it is recommended for them to pay and say goodbye to the participant before the clinician visit, to avoid being accidentally unblinded.

Post-visit:

- Obtain any missing signatures
- □ Score cognitive testing & caregiver forms
- □ Check CALM website for posting of testing results
 - o sac-cu.org on internet explorer-- download "detailed results"
 - Copy the results into the "Safety Labs Template" file in dopamine>Lithium in FTD>Biological Samples, convert the results to numbers in excel (out of range results will highlight in pink), & print
- □ Obtain physician signature on lab results & ECG
- □ Count remaining pills & confirm with expected count. Once done, drop kit off at the NYSPI pharmacy for destruction.
- □ Enter data on REDCap
- Complete Serum-Sham Lithium level form, as described under Weeks 6/8.

Statistical Procedures and Data Analysis.

Outcome measures and covariates. Primary outcome: agitation/aggression score (domain score on the Neuropsychiatric Inventory (NPI), continuous measure from 0-12, longitudinal); Secondary outcome: response (dichotomous, based on 30% decrease in NPI core score (sum of domains for motor activity and agitation/aggression) plus a CGI-C score of much improved or very much improved, longitudinal); Exploratory outcome motor activity score on the NPI. Covariates/Predictor variables: 1) demographic characteristics (e.g., gender, race, age); 2) baseline measures of the corresponding outcomes. Other Measures:1) tolerability, as measured by emergent side effects (TESS scores and adverse events) over the course of the 12 week trial; 2) brain derived neurotrophic factor (BDNF) serum levels.

Sample size and randomization: The randomization will be carried out by the statistician and implemented by the pharmacist, who are both otherwise independent of the research team. The randomization sequences will be balanced in blocks of random size to prevent clinicians from guessing what the next patient's treatment might be.

Modeling longitudinal data and testing hypotheses. Modeling longitudinal data and testing hypotheses. All tests will be two-sided; α =0.05; intent-to-treat with data included for all patients with ≥1 post-baseline assessment. We will use generalized linear mixed models (GLMMs; SAS PROC GLIMMIX) for longitudinal data to evaluate study aims. Models will include fixed effects for treatment group, time, group x time interaction, and any baseline covariates found to be unbalanced despite randomization. Prior to analysis, we will examine all variables at all time points for outliers and inconsistencies and examine their distributions.⁴¹⁻⁴³

Primary hypothesis: *Lithium will significantly reduce agitation/aggression as compared to placebo.*

The following linear mixed effects model will be used: $Y_{ij} = \beta 0 + \beta 1 I T R T + \beta 2t + \beta 3t^* I T R T + \beta 4X_i + \beta 4X_i$ bi + $\epsilon i j$ where Yij is the agitation/aggression score for the *i*th subject at *t*week, *t* =0, 2,...,12, *yi0* is agitation/aggression at baseline, *liTRT* is the indicator variable for randomized condition (placebo vs. lithium), an indicator of recruitment site (Columbia University Medical Center and Johns Hopkins School of Medicine), and any baseline covariates exhibiting imbalance after randomization, bi is a random intercept to account for repeated measures across time within the patient, and $\epsilon i j$ is a random error term. Significant interaction $t^* liTRT$ indicates that the changes in agitation/aggression in each treatment group is different over time (which corresponds to rejecting the null hypothesis that β 3= 0). The effect of time will be estimated for each group separately and the groups will be compared (using contrast) at the last time point t=12. Secondary hypothesis: Lithium will have greater proportion of responders compared to placebo. We will test whether the probability of response by end of active treatment differs significantly in the lithium and placebo groups by a chi-square test. In addition, we will test whether change in the probability of response differs across treatment groups by longitudinal analysis. We will use the generalized linear mixed effects model: logit(Yij) = $\beta 0 + \beta 1$ liTRT+ $\beta 2t$ + $\beta 3t^{*}$ /*iTRT*+ $\beta 4Xi$ + *bi* + ϵij where Yij is the a binary variable indicating response for the *i*th subject at t week, t = 2, 4, ..., 12. We will first test significance of the treatment effect by testing the group by time interaction.

Exploratory Hypothesis. Lithium will significantly reduce repetitive behaviors as compared to placebo. We will use the same model in the analyses for the primary hypothesis where Yij is the motor activity score for the *i*th subject at *t* week, *t* =0, 2,...,12.

Tolerability: We will assess the tolerability of low dose lithium by assessing emergent side effects over the course of the 12-week trial on lithium compared to placebo. We will compute descriptive statistics of tolerability measures in each treatment group and provide both point estimates and their confidence intervals. We will test whether the change in TESS score from baseline to week 12 differs significantly in the lithium and placebo arms by a t-test.

Biomarker Hypothesis. Increases in BDNF serum levels will be associated with decreases in agitation/aggression and repetitive behaviors. The relationship between change in BDNF serum levels (defined as baseline minus endpoint of active treatment) and the changes in agitation/aggression score and motor activity score (defined as baseline minus treatment endpoint) will be tested using correlation analyses.

Power Analysis. Given the proof-of-concept nature of this study as a pilot, effect sizes with 95% confidence intervals rather than statistical significance testing will be the primary results of interest. The overarching aim is to demonstrate feasibility for conducting a larger trial which would then be used to adequately test efficacy.³³ Nevertheless, we provide some guidance regarding the statistical power available for testing differences between treatments. With n=60 patients randomized (30 to lithium, 30 to placebo) we conservatively examine power below assuming attrition will be 20% (i.e. 48 completers) though our past studies have all had attrition <20% and all available longitudinal data will be used for all individuals regardless of whether they complete the 12 weeks. For the primary outcome of agitation/aggression score measured by the NPI, we will have 80% power to detect a medium to large treatment effect size of 0.58-0.83 with the range depending on the within person correlation over time. Additionally, for responder status, we will have >80% power to detect a difference between, for example, a 15% response rate and a 50% response rate at 12 weeks. Differences among other exploratory outcomes and tolerability measures will be detectable with similar power.

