- Medication compliance (the study partner will be asked to count on camera the number of pills remaining in the bottle they used for the first two weeks to ensure correct dosing. 14 pills should remain in the bottle if the medication has been taken for 14 days).

The week 2 visit is estimated to take 60 minutes on average.

Color-codes	
Coordinator	
Physician	
Time	Assessment
20 minutes	Vitals, TESS, Concomitant Meds, CGI,
	with Patient and Caregiver.
10 minutes	Medication compliance review
30 minutes	NPI with Caregiver

At the end of the visit, caregivers should be given new dosing instructions (if the dose has increased, this would be 2 pills/day, one in the morning and one at night) and instructed to switch to a new pill bottle until the next visit (the bottle caps can be labeled with sharpie for ease). The week 4 visit should be scheduled and calendar invitations sent out.

Week 4 Visit

At week 4, the oral dose maybe adjusted from 300 mg/day up to 450 mg/day. This will be based on based on assessments and evaluation of the following:

- Clinical response
- Side effects

The following assessments will be completed at the week 4 visit:

- Concomitant Medications
- Clinical Dementia Rating (CDR)
- CGI Behavior (CGI-S, CGI-C)
- CGI Global (CGI-S, CGI-C)
- NPI
- Stereotypic and ritualistic behaviors
- TESS
- SAS
- Lawson ADL
- Zarit Caregiver Burden Interview.
- Medication compliance (the study partner will be asked to count on camera the number of pills remaining in the bottle they used for the first two weeks to ensure correct dosing.
 0 pills should remain in the bottle if the medication has been taken for 14 days at 300mg/day).

The week 4 visit is estimated to take 70 minutes on average.

Color-codes	
Coordinator	
Physician	
Time	Assessment
20 minutes	Vitals, TESS, Concomitant Meds, Simpson-Angus, CDR, CGI, Lawton with Patient and Caregiver. Lithium Prescription
10 minutes	Medication compliance review
40 minutes	NPI, Zarit with Caregiver

Week 6 Visit

At week 6, blood for serum lithium level will be drawn and the oral dose subsequently adjusted from 450 mg/day up to 600 mg/day if needed. This will be based on the following assessments and evaluations:

- Clinical response
- Side effects
- Blinded lithium level obtained from the unblinded physician

The following assessments will be completed at the week 6 visit:

- Concomitant Medications
- CGI Behavior (CGI-S, CGI-C)
- CGI Global (CGI-S, CGI-C)
- NPI
- Stereotypic and ritualistic behaviors
- TESS

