- Medication compliance (the study partner will be asked to count on camera the number of pills remaining in the bottle they used for the first two weeks to ensure correct dosing. 14 pills should remain in the 2nd bottle if the medication has been taken for 14 days at 450mg/day).

Completed by ExamOne:

- Vital signs
- Serum lithium level
- Safety labs

The week 6 visit is estimated to take 1.5-2 hours on average.

Color-codes	
Coordinator	
Physician	
Time	Assessment
10 minutes	TESS, Concomitant Meds, CGI, with
	Patient and Caregiver.
30 minutes	NPI with Caregiver
10 minutes	Medication compliance review

Vital signs and blood draw will be scheduled separately and completed by the Exam One mobile phlebotomy team, who will ship samples directly to the CALM lab for processing.

Week 8 Visit

At week 8, blood for serum lithium level will be drawn and the oral dose subsequently adjusted up to 600 mg/day if needed based on the following assessments and evaluations:

- clinical response
- side effects
- Blinded lithium level from the unblinded physician.

The following assessments will be completed at the week 8 visit:

- Concomitant Medications
- CDR
- CGI Behavior (CGI-S, CGI-C)
- CGI Global (CGI-S, CGI-C)
- NPI
- Stereotypic and ritualistic behaviors
- TESS
- SAS
- LADL
- Zarit Caregiver Burden Interview.
- Medication compliance (the study partner will be asked to count on camera the number of pills remaining in the bottle they used for the first two weeks to ensure correct dosing.
 0 pills should remain in the 2nd bottle if the medication has been taken for 14 days at 600mg/day).

Completed by ExamOne:

- Vital signs
- serum lithium level

The week 8 visit is estimated to take 50 to 60 minutes on average.

Color-codes	
Coordinator	
Physician	
Time	Assessment
20 minutes	TESS, Concomitant Meds, Simpson-
	Angus, CDR, CGI, Lawton with Patient
	and Caregiver. Lithium Prescription
40 minutes	NPI, Zarit with Caregiver
10 minutes	Medication Compliance Review

Vital signs and blood draw will be scheduled separately and completed by the Exam One mobile phlebotomy team, who will ship samples directly to the CALM lab for processing.

Week 10 Visit

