- Review next steps: 1) confirmation of eligibility after lab results are returned, 2) shipment of study drug and phone call once it arrives (it is good to go over the starting dosing schedule / potential side effects at this time as well), 3) scheduling of week 2 virtual visit 2 weeks after study drug arrives.

Post-visit:

- Obtain any missing signatures
- □ Score cognitive testing & caregiver forms
- □ Fill in any incomplete documents (e.g. inclusion/exclusion) to the best of your ability
- Check CALM website for posting of testing results
 - o sac-cu.org on internet explorer-- download "detailed results"
 - Copy the results into the "Safety Labs Template" file in dopamine>Lithium in FTD>Biological Samples, convert the results to numbers in excel (out of range results will highlight in pink), & print
- □ Obtain physician signature on lab results & ECG
- Prepare pharmacy referral form to send to pharmacy once inclusion/exclusion criteria met (get physician signature & scan). See "Randomization" section for sample email.
- Organize forms in new participant binder or folder
- □ Enter data on REDCap- you will need to use both "screening" and "week 0" tabs

- □ Complete MHLS form (if surrogate signed consent) & email to IRB, print and put in participant binder / regulatory binder, and mail or fax to the NY office of Legal Services.
- □ Complete **study drug issue/return log** once the participant receives the drug kit. For this log, note that each kit contains 12 medication bottles. Each bottle contains 28 pills and is labeled by week (#1-12). Each pill is 150mg of study drug.
 - Under "Study Drug Bottle ID", put "LF1XX Week(s) X" to denote the bottle you are instructing the participant to use up until the next study visit (in this case it would be LF1XX Week 1).
 - For number of pills dispensed, indicate the number of pills in the bottle(s) you are instructing the participant to use. You will refer to these bottles at the following visit when you fill in information for study drug returned, and will include the pills remaining in the previously specified bottle as "pills returned".
 - For dose recommended, write the daily dose in mg.
 - It is important to instruct the participant to begin a new bottle after each study visit, regardless of whether pills remain in the old bottle. While taking 150-300mg/day, participants will only need one bottle between visits, but when taking 450-600mg/day, they will need two.

Week 2

Pre-visit:

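### At remote visits ending an interval on 300 or 600 mg/day, the expected pill count of 0 is also the lowest possible count, so over-use drawn from another bottle passes as correct dosing

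*Combined protocol and SAP*

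**What the plan says.** The study drug log instructions (Visit Checklists, Screening / Baseline, Post-visit) state that "each kit contains 12 medication bottles. Each bottle contains 28 pills" and that "Each pill is 150mg of study drug". One bottle is assigned between visits at 150-300 mg/day and two at 450-600 mg/day. A new bottle is started after every visit even if the old one is not empty. The whole kit is shipped to the home (Randomization).

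At each remote visit the partner counts on camera what is left in the bottle in use. The purpose given is to make sure dosing was correct. The expected values are:

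- Week 4 Visit: "0 pills should remain in the bottle if the medication has been taken for 14 days at 300mg/day".
- Week 8 Visit: "0 pills should remain in the 2nd bottle if the medication has been taken for 14 days at 600mg/day".
- Week 2 (150 mg/day) and Week 6 (450 mg/day): 14 pills.
- Week 10 Visit: only the 450 mg/day figure, again 14.

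The Week 4 checklist ties its 0 to a 14-day interval. The Week 6, 8 and 10 checklists tell the coordinator to "calculate the number of pills that should be remaining based on dose & time since the last visit". In the log, the coordinator "will include the pills remaining in the previously specified bottle" as the pills returned. At week 12 the used kit and all remaining pills come back and are counted against the expected number.

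**The concern.** A count detects over-use only if it can fall below its expected value. At 300 and 600 mg/day the expected value is 0, so it cannot. A participant who takes more than assigned empties the same bottles, draws the extra from one that nobody counts, and produces the reading of a participant who dosed correctly.

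At stake are safety monitoring and the accuracy of the adherence record. The drug's serum level is monitored for safety, the whole supply is at home, and the count is the manual's stated check on correct dosing. At week 4 no lithium draw is routinely scheduled. At week 10 none is planned unless the dose was raised at week 8. At those two visits the count is usually the only objective check on intake.

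**Working it through.** **Inputs.** 28 pills per bottle, 150 mg per pill, 12 bottles per kit, one bottle assigned at 150-300 mg/day and two at 450-600 mg/day (study drug log instructions).

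**Step 1: reproduce the manual's counts.** Remaining = bottles × 28 − (dose/150) × 14.

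| Dose (mg/day) | Assigned pills | Used in 14 days | Remaining | Supply lasts |
|---|---|---|---|---|
| 150 | 28 | 14 | 14 | 28 days |
| 300 | 28 | 28 | 0 | 14 days |
| 450 | 56 | 42 | 14 | 18.7 days |
| 600 | 56 | 56 | 0 | 14 days |

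All the stated remote-visit counts reproduce. At week 10 on 600 mg/day the checklist calculation also gives 56 − 56 = 0.

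**Step 2: over-use at day 14.**

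- Assigned 2 a day, takes 3: 3 × 14 = 42 against 28 (150%). The assigned bottle reads 0; 14 pills came from elsewhere.
- Assigned 4 a day, takes 5: 5 × 14 = 70 against 56 (125%). The assigned bottles read 0; 14 came from elsewhere. The log shows 56 dispensed and 0 returned.
- By contrast, one extra pill a day at 150 or 450 mg/day leaves 0 where 14 are expected, which is visible.

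**Step 3: pills available outside the count.** Full titration uses 14 × (1 + 2 + 3 + 4 + 4 + 4) = 252 pills. The kit holds 12 × 28 = 336, so 84 are surplus. During weeks 6-8, pills at home outside the two assigned bottles number 336 − (14 + 28 + 42) − 56 = 196. The 14 left from the first bottle would by themselves cover either example in Step 2.

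**Step 4: visits after day 14.** Expected count at 600 mg/day = 56 − 4 × days.

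| Day | Expected count | Doses covered by the assigned 56 |
|---|---|---|
| 15 | −4 | 56/60 = 93.3% |
| 16 | −8 | 56/64 = 87.5% |
| 17 | −12 | 56/68 = 82.4% |

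At 300 mg/day the expected count falls by 2 per day late and the percentages are the same. A participant who stopped when the bottles ran out and one who opened another bottle to stay on dose both show 0. No instruction covers a negative expected value.

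**Step 5: what the count still detects.** Missed pills at an on-time visit leave a positive remainder. At an early visit some over-use can show: on day 12 the expected count is 28 − 24 = 4 at 300 mg/day and 56 − 48 = 8 at 600 mg/day.

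**Step 6: intervals affected.** On full titration the zero-margin intervals ending at a remote visit are those ending at weeks 4, 8 and 10.

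**Step 7: the week 12 benchmark.** The Week 12 Visit section equates four bottles with 128 pills. At 28 per bottle, 4 × 28 = 112, and 28 days × 4 pills = 112. A total of 128 would need 32 per bottle. Used as the benchmark, 128 would let 128 − 112 = 16 excess pills pass.

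**The case against.** Hidden over-use requires opening bottles that were not assigned, against instructions and week labels, and caregivers are the ones instructed on dosing. Serum lithium is measured at weeks 6, 8 and 12, TESS is completed at every follow-up visit, and caregivers are asked to confirm the dosage when appointments are confirmed. The week 12 kit count can expose a net discrepancy. Excess taken from bottles next assigned at 450 mg/day can surface as a shortfall, because 14 are expected there.

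All of this is fair, and it limits the point without removing it. Real serum levels inform only on the lithium arm; placebo sham levels are themselves built largely on the number of pills taken. TESS and caregiver confirmation are indirect. The week 12 count comes after trial dosing ends, cannot place an error in an interval, and lets over-use offset under-use. The shortfall route does not help across consecutive 600 mg/day intervals, where 0 is expected again.

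A reader might infer four stronger things, which the documents do not support:

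- *Under-use before a late visit reads as perfect adherence.* It does not. The 0 is stated for 14 days, and the Week 6, 8 and 10 checklists adjust for elapsed time, so at day 17 a 0 is set against −12. It is uninterpretable, not a match.
- *The manual's loose two-week timing creates late visits at these doses.* That wording (Randomization) concerns the Week 2 visit, at 150 mg/day. Better evidence that intervals may vary is the 14-day condition in the Week 4 checklist and the elapsed-time instruction in the later ones.
- *Four of six intervals go unchecked.* On full titration four have zero margin, but the one ending at week 12 closes with the whole-kit count. Three lack it.
- *The trial's results depend on this record.* Dose adjustment is described in terms of response, side effects and, from week 6, lithium level. The analysis is intent-to-treat with no adherence term.

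**Conclusion.** The point holds for remote visits that end an interval on 300 or 600 mg/day. At an on-time visit, over-use drawn from an uncounted bottle gives exactly the expected 0; in the worked cases 125% and 150% of the assigned pills are recorded as full adherence. At a late visit, 0 cannot be interpreted. Three intervals (6 of 12 weeks) are affected on full titration, with no whole-kit check when they end.

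This assumes full titration, which the Introduction makes conditional; a participant held at 150 mg/day would not be affected. It also assumes that the extra pills come from a bottle not counted at that visit. The documents give no figure for how often over-use or late visits occur, so the size is what the count can miss, not an expected error rate. The consequence is confined to safety monitoring and the adherence record. It is a worthwhile low-cost improvement and does not threaten the efficacy analyses.

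**What to change.** In the medication compliance lines of the visit sections, the visit checklists and the study drug log:

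1. At each remote visit, count every opened bottle and have the study partner show on camera that all the others are unopened.
2. Log cumulative pills used (336 minus pills remaining) against the sum of prescribed pills per day times actual days.
3. Note any unassigned bottle that was opened because the visit was late.
4. Reconcile the Week 12 Visit figure of 128 pills for four bottles with the 28 per bottle in the log instructions.

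This separates the cases above. At week 8 on full titration with on-time visits, 336 − (14 + 28 + 42 + 56) = 196 pills should remain. The participant who took 5 a day in weeks 6-8 would show 196 − 14 = 182. If that visit fell on day 17, the one who ran out would show 196 and the one who stayed on dose 196 − 12 = 184.

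The cost is one more log column and, by my assumption, a few minutes within the 10-minute compliance review already scheduled. It adds no visit or staff and changes no dosing rule. What a participant should do when assigned bottles run out before a late visit is a dosing instruction for the sponsor to settle; none is proposed here.
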